Study Protocol and Statistical Analysis Plan

Title: Cook Balloon vs Dilapan-S for Outpatient Cervical
Ripening

NCT05062343

Document date 10/24/2022

Institutional Review Board Intervention/Interaction Detailed Protocol

Principal Investigator: [name] MPH

Project Title: A Randomized Controlled Trial Comparing Cook Balloon and Dilapan-S for Outpatient Cervical Ripening

Version Date: 10/24/2022

For Intervention/Interaction studies, submit a Detailed Protocol that includes the following sections. If information in a particular section is not applicable, omit and include the other relevant information.

1. Background and Significance

In August 2018, the ARRIVE trial was published in the New England Journal of Medicine. This large, multicenter, randomized, controlled trial showed that elective induction of labor (IOL) at 39 weeks' gestation reduced the c-section rate, when compared to expectant management (awaiting labor until 41 weeks or other medical indication for induction arose) with a decrease in hypertensive disorders of pregnancy and no increase in neonatal or maternal morbidity or mortality¹. Since then, demand for elective IOL has been increasing nationwide²; however, while IOL was shown to have many positive benefits, it does lead to longer admission on labor and delivery when compared to spontaneous labor, and many labor and delivery units do not have the physical resources (rooms, nurses) to accommodate this surge in induction²⁻³.

Given this strain on resources, research has turned to identifying safe, effective outpatient methods for the initial steps of IOL, termed "cervical ripening"³⁻⁵. Cervical ripening prepares the cervix for induction of labor with Pitocin, a synthetic oxytocin. Pitocin is most effective after the cervix has already started to dilate and thin out, or efface, as Pitocin receptors are upregulated during this "ripening" phase.

Both the Cook Balloon (Figure 1), a dual balloon mechanical cervical dilator, and Dilapan-S (Figure 2), a synthetic osmotic cervical dilator, are FDA approved for cervical ripening. Both have been shown to be effective inpatient agents of cervical ripening⁶. Most outpatient cervical ripening to date has been studied in mechanical balloon devices, either Foley catheter or Cook balloon⁴⁻⁵. Dilapan-S has been more commonly used for outpatient cervical dilation prior to dilation and evacuation or other gynecologic procedures⁷ and patients and providers are less familiar with it for pre-induction of labor cervical ripening. Both the Cook catheter and Dilapan-S are already approved agents of outpatient cervical ripening at Brigham and Women's Hospital. This study will be the first to compare Dilapan-S and the Cook catheter directly in the outpatient setting. Currently, the choice of outpatient ripening agent (mechanical ripening with a Cook balloon or Dilapan-S or pharmacologic ripening with misoprostol) is at the provider's discretion at Brigham and Women's Hospital. Our study will help providers and patients make informed choice about the optimal mechanical ripening agent in the outpatient setting.

Figure 1. Cook Balloon for cervical ripening. A. Catheter with both uterine and vaginal Balloon Inflated. B. Cook Balloon in place with uterine balloon and vaginal balloon inflated and “ripening” the cervix.

[figure not shown]
[figure not shown]

Figure 2. Dilapan-S. A. Demonstration of the increase in diameter Dilapan-S undergoes due to osmotic dilation. B. Dilapan-S in place in the cervix.

2. Specific Aims and Objectives

Specific Aim 1: To determine if Dilapan-S is not inferior to Cook balloon for outpatient cervical ripening. ***We hypothesize that Dilapan-S is non-inferior to Cook balloon for cervical ripening, as measured by change of Bishop score.***

Specific Aim 2: To determine with which method of outpatient cervical ripening patients are more satisfied. ***We hypothesize that patients will be more satisfied with their experience with Dilapan-S when compared to the Cook Catheter.***

3. General Description of Study Design

This study will be a randomized controlled trial with 1:1 randomization.

Clinic visit for term (37-41 6/7 week) pregnant patients 18-50 years old with decision by primary obstetrics provider for induction of labor and patient is deemed candidate for outpatient cervical ripening per BWH Cervical Ripening Protocol by their primary obstetrics provider

- Inclusion:
 - Vertex presentation
 - Induction of labor indicated for maternal or neonatal reasons
- Exclusion
 - Prior cesarean section
 - Non-English-speaking participants
 - No need for cervical ripening (Bishop score >6, >2cm dilated)

Patient is scheduled for outpatient cervical ripening per BWH protocol. Her outpatient obstetrical provider informs her of the study. Study staff will attempt to contact patient once appointment is made and discusses study with patient and answer any questions she may have. If patient is unable to be contacted they will still be approached for the study when they arrive for outpatient cervical ripening after study has been introduced by a clinician/provider at their visit.

At time of her cervical ripening appointment on CWN 3, CWN 5 labor and delivery, or at [name] if patient remains interested, she is consented by physician investigators. Questions answered.

RANDOMIZATION: 1:1 Cook catheter Vs Dilapan-S per outpatient protocol.

Cervical ripening with either agent per randomization.

If unable to place cervical ripening device, further cervical ripening per provider preference by one of options already approved per BWH outpatient cervical ripening protocol

Return to L&D within 24hrs of device placement (return visit will be scheduled through hospital EMR as is current BWH outpatient cervical ripening protocol) or earlier with any concerning symptoms (vaginal bleeding, fever, rupture of membranes, labor, decreased fetal movement, etc), as detailed in existing BWH outpatient cervical ripening protocol

When returned to L&D, device removed or confirmed expelled. Sterile vaginal exam performed by blinded examiner (3rd year, chief resident, or further in training- i.e. Fellow or Attending), blinded to study arm.

Paper patient satisfaction survey to be given to patient at this time by study staff for written completion by subject

Further induction of labor per primary labor and delivery team.

4. Subject Selection

Our study population will include women 18-50 years of age at term (37-41 6/7 weeks gestational age) who are low risk (i.e. without any maternal or fetal co-morbidity) and with a singleton gestation in cephalic presentation who are candidates for outpatient cervical ripening per the Brigham and Women's outpatient cervical ripening protocol (Appendix A). Both nulliparous and multiparous women will be included. Women will need to have a bishop score <6 or cervical dilation <2cm with intact membranes to be included, as these are the women currently being offered outpatient cervical ripening prior to labor induction. Women will be excluded if there is a contraindication to outpatient cervical ripening per Brigham and Women's outpatient cervical ripening protocol (Appendix A) or contraindication to vaginal delivery. Women with history of a prior cesarean section will be excluded given their management may differ after cervical ripening. Non-English-speaking women will also be excluded given lack of study staff ability to communicate in languages other than English and lack of guaranteed 24/7 interpreters. Women who are patients of study investigators will be eligible for enrollment. This vulnerable population will be protected from coercion by giving patients a consent form to review at home prior to actual study enrollment and by encouraging patients to discuss the study with other healthcare professionals.

Women will be recruited from all practices that deliver at the Brigham, including Maternal Fetal Medicine, general Obstetrics clinics, private practice groups, and midwifery groups at Brigham and Women's Hospital. By recruiting from all of the delivering groups at BWH, we should be enrolling a diverse patient population.

5. Subject Enrollment

Women will be booked for outpatient cervical ripening per their primary obstetrics provider. Typically, cervical ripening is scheduled by the primary provider within the week prior. Outpatient ripening is currently performed by a variety of methods (Cook balloon, Dilapan-S and misoprostol) at the primary provider's discretion. The eligibility for each of these methods is the same, thus all patients scheduled for outpatient ripening in current clinical practice are potentially eligible for this study. At the time patients are scheduled, the scheduling provider (nurse or MD) may inform the patient about the study. The scheduling provider will then let the study staff know if patients are interested and if they would like to be contacted for further information or if they are not interested and would prefer not to be further contacted by study staff. Study staff will attempt to contact interested patients to answer any questions they have about the study. This will not be a pre-screening call as anyone who is scheduled for outpatient cervical ripening is eligible for the study. Study staff will also monitor the outpatient ripening appointments booked through the EPIC schedule. Study staff will contact patients who are scheduled for outpatient cervical ripening appointments within 48 hours of their appointment via telephone to discuss the study and answer any questions and assess interest. If the patient is unable to be contacted, a clinician/provider at their cervical ripening visit will introduce the study to the patient and if they agree to be approached, study staff will then approach them for possible enrollment. Once the patient arrives for their scheduled outpatient cervical ripening appointment on CWN3, CWN5 Labor and Delivery triage, or [name] study staff will review the study, answer any questions and informed consent will be obtained. If the patient had not heard about the study previously, a provider/clinician will introduce the study to the patient when patient arrives and ask if study staff can approach them. If the patient agrees,

study staff will then discuss the study in more detail, answer any questions, then will step away while NST is being performed (20-30 minutes) to allow for contemplation then will re-approach the subject to confirm if they are or are not interested in the study after NST is complete. After it is confirmed that the patient is still candidate for outpatient cervical ripening per standard practice at Brigham and Women's, which requires the non-stress test fetal heart tracing to be reactive, an exam to confirm the cervix needs ripening (Bishop score < 6 and cervix < 2cm dilated) and an ultrasound to confirm cephalic presentation, they will be randomized to either Dilapan-S or Cook balloon in a 1:1 ratio.

At the time of enrollment, patients will be assured that they will receive standard of care treatments whether or not they are in the study and enrollment will not affect their care.

Only adults will be included in the study. Study will be limited to English speaking patients as enrollment may happen day or night and on weekends (given outpatient cervical ripening schedule on labor and delivery) when interpreters may not be available. No surrogate decision makers will be allowed to consent for patients.

A random number generator will be used to randomize women in blocks of 6 with stratification based on parity (patients who have had a vaginal delivery before or not).

As randomization will occur after sterile vaginal exam, the examiner obtaining the initial exam will be blinded to which arm of the study the patient will be in as the exam will be recorded prior to randomization. The patient will not be blinded as the devices are different in placement and post-placement.

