If the patient satisfaction survey is not completed during the delivery admission, it may be collected anytime the patient returns to the hospital for routine prenatal care until the 6 week postpartum visit.

7. Risks and Discomforts

Women may experience discomfort with either Cook catheter or Dilapan-S insertion, though there is no increased risk from the standard BWH outpatient cervical ripening protocol.

Because both the Cook catheter and Dilapan-S are both routinely used for outpatient cervical ripening, we think that there is minimal increased risk from the study versus routine standard of care for outpatient cervical ripening.

8. Benefits

There is no direct benefit to individuals. There are however many benefits for the healthcare system in the future. By determining that Dilapan-S is noninferior to Cook catheter for outpatient cervical ripening we will be increasing provider awareness of an effective method of cervical ripening. Healthcare cost would benefit from the information gained in this study by potentially increasing outpatient cervical ripening which could decrease hospital stays. Currently, the most effective method of inducing labor remains unknown.

9. Statistical Analysis

The main outcome will be change in Bishop score. We will collect any information about outcomes regarding maternal or neonatal morbidity until four weeks from delivery. The patient satisfaction survey may be administered until the 6-week postpartum visit. Once these items are collected, patient participation will end.

Bishop score is defined by 5 components (Figure 3) all assessed during a sterile vaginal exam. These individual scores are then combined into a single score (0-13) to determine the Bishop score. Our

outcome of interest is change in Bishop score to be calculated as Bishop score after cervical ripening minus Bishop score prior to cervical ripening.

Figure 3. Bishop score. Final score is a sum of the 5 individual scores.

Score	Dilation (cm)	Position of Cervix	Effacement (%)	Station (-3 to +3)	Cervical Consistency
0	Closed	Posterior	0-30	-3	Firm
1	1-2	Mid-position	40-50	-2	Medium
2	3-4	Anterior	60-70	-1,0	Soft
3	5-6	--	80-100	+1 to +3	--

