APPENDIX A: Brigham and Women's Outpatient Cervical Ripening Protocol

Medical Staff Note...

**OBSTETRICS AND GYNECOLOGY
BRIGHAM AND WOMEN'S HOSPITAL**

DATE: 12/21/2020 **Updated June 17, 2021** # 2313

TO: Medical Staff

FROM: [name], [name], [name], [name], [name],
[name], [name], [name]

RE: **Office-Based Ambulatory Cervical Ripening Protocols**

Updates June 17, 2021

GBS positivity is no longer an exclusion for office-based ambulatory cervical ripening using a mechanical method of cervical ripening, including Foley or Cook balloons, Dilapan or laminaria cervical dilators.

Mild polyhydramnios is not an exclusion for office-based ambulatory cervical ripening.

Well-controlled GDM, with or without medications, is not an exclusion for ambulatory office-based cervical ripening.

Background: As noted in a recent Medical Staff note from [name] (**Cervical Ripening and Induction of Labor in Nulliparous Patients before Forty Weeks' Gestational Age, #2304**) clinical practice

is evolving to increase the use of office-based ambulatory cervical ripening as the **initial step** for induction of labor in low-risk women from 39 weeks and 0 days gestation through 39 weeks and 6 days gestation. **One day of office-based ambulatory cervical ripening is an important part of a multi-step process that is followed by additional ambulatory (CWN5 Triage) or inpatient cervical ripening, if needed, and oxytocin induction of labor.**

At BWH we have years of experience with office-based ambulatory cervical ripening using oral misoprostol. Office-based ambulatory mechanical cervical ripening with a balloon catheter (Foley or Cook catheters) or Dilapan (hygroscopic cervical dilator) are also effective and safe methods (Alfirevic 2020, Dong 2020, Yang 2018, Saade 2019). Mechanical methods are particularly suitable for the office-based ambulatory setting as they are not generally associated with an increased risk of tachysystole.

The choice of office-based ambulatory cervical ripening agent is at the provider's discretion. However, we encourage the following:

- (1) First line: Balloon cervical ripening (30 cc Foley or Cook balloon)
- (2) Second line: Dilapan-hygroscopic cervical dilator
- (3) Third line: Oral misoprostol

At this time, we are not endorsing the use of dual agents in the office-based ambulatory setting (e.g. balloon or Dilapan plus misoprostol).

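### A single printed block size of 6 would let anyone keeping a within-stratum tally foresee up to 23% to 25% of allocations before the baseline Bishop exam

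*Combined protocol and SAP*

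**What the plan says.** Section 5 (Subject Enrollment) says that "A random number generator will be used to randomize women in blocks of 6 with stratification based on parity", the two strata being "patients who have had a vaginal delivery before or not". On allocation, "they will be randomized to either Dilapan-S or Cook balloon in a 1:1 ratio", so each block holds three of each device. No other block size is mentioned. The section does not say who holds the list or how it is concealed.

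On blinding, Section 5 states that "the examiner obtaining the initial exam will be blinded to which arm of the study the patient will be in", and the only reason given is that "the exam will be recorded prior to randomization". It adds: "The patient will not be blinded as the devices are different in placement and post-placement".

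The baseline exam has two uses. Sections 5 and 6 make it an eligibility check, and Section 9 makes it half of the primary endpoint: "outcome of interest is change in Bishop score to be calculated as Bishop score after cervical ripening minus Bishop score prior to cervical ripening". Section 6 (Study Procedures) places consent after this exam, whereas Section 5 reads as if consent comes first. Section 3 has physician investigators take consent, and Section 4 allows investigators to enrol their own patients. Sections 3 and 6 keep the return examiner unaware of the device. No comparable separation is described for the baseline examiner.

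**The concern.** Recording the baseline exam before randomisation protects it only if the next allocation cannot be foreseen. With a constant, published block size and distinguishable devices, the end of a block can be deduced: once three women in a block have been allocated one device, the rest must receive the other.

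Foreknowledge could act in two ways. It could influence which women are approached or consented, particularly if consent follows the exam as in Section 6. It could also influence the baseline Bishop score, which includes judged components such as consistency and position. Because the endpoint is a simple difference and Section 9 names adjustment for parity only, each point of baseline shading passes in full into the change score. The blinded return exam cannot undo it.

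**Working it through.** **The plan's own figures.** The documents give no figure for predictability. The illustration below uses the Section 9 inputs: margin 2, SD 3, two-sided 0.05, 80% power, 39 per arm raised by 15% to 45. The normal formula gives 2 × (3 × (1.960 + 0.842)/2)² = 35.3, so 36 per arm, and the t distribution gives 37. Dividing 37 by 0.955 (the Wilcoxon efficiency under normality, my assumption, in keeping with the planned non-parametric analysis) gives 38.7, so 39. Then 39 × 1.15 = 44.85, so 45 per arm and 90 in total. These figures do not depend on the blocking.

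**Certain allocations in a block of 6.** There are 20 orderings of three and three. An allocation is certain once one device's three places are used.

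| Place in block | 1 | 2 | 3 | 4 | 5 | 6 | Sum |
|---|---|---|---|---|---|---|---|
| Probability of certainty | 0 | 0 | 0 | 2/20 = 0.1 | 8/20 = 0.4 | 1 | 1.5 |
| Best guess correct | 0.5 | 0.6 | 0.6 | 0.7 | 0.7 | 1 | 4.1 |

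So 1.5/6 = 25.0% are certain, and 4.1/6 = 68.3% can be guessed correctly, against 50% without knowledge.

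**Over 90 women in two strata.** If both strata end on complete blocks, 15 × 1.5 = 22.5 are certain (25.0%). With 45 in each stratum, each has seven full blocks and three further places: 2 × 7 × 1.5 = 21.0 (23.3%). Best-guess accuracy is then (7 × 4.1 + 1.7)/45 = 67.6%.

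**Varying block sizes.** This was simulated with 45 women per stratum, sizes 4, 6 and 8 equally likely, and an observer who knows the set of sizes and every earlier allocation but not the order of sizes. About 2.3% of allocations are certain and 67.4% are guessed correctly. The same simulation with fixed blocks of 6 gives 23.2% and 67.6%, which agrees with the exact values.

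**What shading could do (illustration).** Assume the baseline is misjudged by 0.5 to 1 point in the known quarter. One arm's mean change then moves by 0.25 × 0.5 = 0.125 to 0.25 × 1 = 0.25. Opposite shading in both arms moves the arm difference by 0.25 to 0.5. With 45 per arm, SE = 3 × √(2/45) = 0.632. At a true deficit of 2, the false non-inferiority rate is 1 − Φ(1.96 − shift/0.632), with shift positive when it favours Dilapan-S.

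| Assumed shading | Shift | False non-inferiority |
|---|---|---|
| None | 0 | 2.5% |
| One arm, favouring Dilapan-S | +0.125 to +0.25 | 3.9% to 5.9% |
| Both arms, favouring Dilapan-S | +0.25 to +0.5 | 5.9% to 12.1% |
| Both arms, favouring Cook | −0.25 to −0.5 | 0.9% to 0.3% |

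In the last row the cost is power. At no true difference, Φ((2 + shift)/0.632 − 1.96) falls from 88.5% to 79.0% (shift −0.25) or 66.0% (shift −0.5).

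**The case against.** The case for leaving the plan alone is that the tally is hard to keep.

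- Sections 1 and 5 say both devices are already used outside the trial at the provider's choice, so seeing a device does not identify a trial allocation.
- Sections 3 and 5 name several locations, Section 4 recruits from all delivering practices, and Section 5 expects enrolment by day, night and weekend.
- Section 9 expects about 10% placement failures, and Section 3 then allows another approved method, so the device seen is not always the one allocated.
- Section 6 has the baseline exam done as routine. Nothing says that the examiner is an investigator or knows earlier allocations.

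All of this stands, and it makes 23% to 25% an upper bound. It does not close the gap, because the plan neither rules out such a tally nor separates the baseline examiner from staff who might have one.

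A reader might also infer that staff preference would produce a false non-inferiority finding, since Appendix A ranks "First line: Balloon cervical ripening (30 cc Foley or Cook balloon" ahead of Dilapan. The documents do not support that. A preference for the balloon would lower the Cook baseline, enlarge the Cook change and work against Dilapan-S. The trial's own hypothesis of non-inferiority could pull the other way, but no document shows that either influence acts on the exam.

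Nor is 12.1% an expected error rate. It requires a perfect tally, a full point of shading in every known case, both arms shaded in opposite directions, and all of it favouring Dilapan-S. Upward shading is further limited because the baseline score must stay below 6 for the woman to be eligible.

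**Conclusion.** The point holds as a vulnerability in allocation concealment that is cheap to remove. Up to 23% to 25% of allocations (21 to 22.5 of 90) are certain to someone who knows the block size and has a complete tally within the parity stratum. It does not follow that a quarter of allocations will in fact be foreseen, since the documents do not say who could do it. Nor do they show that any baseline score or consent decision would be biased.

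The direction of any bias is unknown. The error rates above rest on an assumed shading of 0.5 to 1 point applied to the whole known quarter, a normal approximation, SD 3 and 45 per arm. They show that the false non-inferiority rate could move either way from 2.5%. Selective approach or consent was not quantified.

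**What to change.** In Section 5, replace the fixed block size with wording such as: *randomly permuted blocks of randomly varying size within parity stratum; block sizes and the allocation list are held in a separate document not available to staff who approach, consent or examine women.* Do not print the sizes in the protocol. Apply the new list to women not yet randomised.

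With sizes such as 4, 6 and 8, certain allocations fall to about 2% even if the set of sizes becomes known. Best-guess accuracy hardly changes (near 67%), so the gain is the removal of certain knowledge. To address the remainder, Section 6 could also ask for a baseline examiner who does not know earlier trial allocations, where staffing allows.

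The cost is a new list and one sentence. The largest possible final imbalance per stratum rises from 3 to 4 (half of the largest block). The sample size is unchanged.
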